Participants: Up to 25 adult patients who are at least 18 years of age with hemicrania continua will be enrolled into the screening phase of this study at Mayo Clinic Arizona. Enrollment will stop once 25 subjects provide headache diary during the screening phase that meets eligibility criteria (i.e. meet diagnostic criteria for hemicrania continua). Exclusion and inclusion criteria will be modeled after those used in the phase 2 and 3 trials of erenumab for the prevention of migraine and adapted for the diagnosis of hemicrania continua.^{10,11} Potential participants will be excluded if they have active chronic pain conditions other than hemicrania continua (e.g. chronic pelvic pain) or acute pain conditions (e.g. recent surgery).

Subject Eligibility

Inclusion Criteria

- Adults ages 18 and over
- At least a 12 month history of hemicrania continua according to International Classification of Headache Disorders, 3rd Edition (ICHD-3)¹
- Previous or current complete response to indomethacin
- Stable preventive treatment for at least 2 months and no anticipated need to adjust/add current headache prevention treatment

Exclusion Criteria

- Nonresponse to a therapeutic dose of indomethacin for hemicrania continua when used for at least 1 week
- Pregnant or lactating subjects
- Use of barbiturate or opioid >6 days per month; history of chronic migraine
- History of previous trigeminal-autonomic cephalgia

- History within previous 2 months of interventional procedure for headache (occipital or other extracranial nerve block, sphenopalatine ganglion block, cervical facet block, facet rhizotomy)
- History of cranial nerve/rhizolysis
- Botulinumtoxin injection within previous 4 months
- Parenteral infusion of an oral corticosteroid use for more than 3 days within 4 weeks prior to screening phase

Screening Phase (1 week) (Day -7)

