Erenumab will be stored refrigerated at 2°C to 8°C (36°F to 46°F) until time of use. Once removed from the refrigerator, it will be kept at room temperature and used within 7 days. Prior to administration, erenumab will sit at room temperature for at least 30 minutes, protected from direct sunlight.

Daily Headache Diary

A daily headache diary will be completed for the next 4 weeks to allow for assessment of changes in headache frequency and intensity. Headache diary data will be analyzed to classify patients as “responders” (50% or greater reduction in headache frequency at week 4 post erenumab treatment compared to frequency during the screening phase) or “non-responders” (less than 50% reduction in headache frequency at week 4 post erenumab treatment compared to the frequency during the screening phase). Since patient outcomes will be measured at 4 weeks (opposed to 12 weeks like it is done in the majority of clinical trials), depending upon patient outcomes other definitions of “response” and “non-response” could be used.

Acute Headache Therapy: Patients will be allowed to use acute headache treatments including NSAIDs during the study if needed. The use of these treatments will be recorded.

Table: Schedule of Events

	Screening Phase (7 days) (Day -7)	Baseline Visit (Day 0)	Weekly, weeks 1-4 (Day 0 to Day 28)	Follow-up Visit, week 4 (Day 28)	Safety follow-up visit, week 8 (Day 56)
Visit Window (days)	-2	+/- 0	n/a	+/- 3	+/- 3
Eligibility: I/E criteria	X				
Vital signs	X	X		X	X
Demographics, PMH	X				
Urine pregnancy test	X	X			
Headache characteristics	X			X	X
Concomitant medications / treatments	X			X	X
BDI		X		X	
STAI		X		X	
MIDAS		X		X	
PGIC				X	
Adverse events			X	X	X
Headache diary, daily	X		X		
Treatment: Erenumab injection		X			

Sample Size

A sample size of 20 will have 80% power to detect a decrease of frequency of headache days (in 28-day period) of 2 or more from baseline, assuming a standard deviation of 3, using a paired t-test with a 0.05

two-sided significance level. It is anticipated that up to 25 patients will be enrolled in the study in order to obtain 20 evaluable patients for the primary outcome.

Subject Recruitment and Screening

Subjects will be recruited from the Mayo Clinic Arizona Headache and Neurology clinics, from the clinical practices of colleagues practicing in the Phoenix region, and via posting of IRB-approved recruitment materials.

Subject Compensation

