This is a prospective, open-label, study of patients with hemicrania continua treated with a single dose of erenumab 140 mg SQ. Estimates of efficacy (decrease in frequency of headache) will be assessed. For the primary endpoint, patients will be classified as a responder (50% or greater reduction by week 4 post erenumab treatment) or a non-responder (less than 50% reduction in headache frequency). SAS version 9.4 (SAS Institute, Cary, NC) will be used for analysis. The analysis will be kept descriptive and efficacy will be evaluated based on clinical meaningfulness threshold.

Analysis Plans

Primary endpoint & analyses: All eligible patients that successfully complete the screening phase and have initiated treatment with erenumab will be considered evaluable for assessing the primary endpoint. The primary endpoint of this trial will consist of the proportion of patients who are considered to have a response as defined above at the end of week 4 divided by the total number of evaluable patients on the study. Patients will not be considered evaluable if they did not complete the screening phase requirements or discontinued the study due to withdrawal before receiving erenumab. A point estimate and two-sided 95% confidence interval will be computed for this endpoint based on properties of the binomial distribution.

The analysis plan for additional (secondary) endpoints are listed below.

Headache days (>4 hours moderate/severe pain) weeks 4 compared to baseline: Change in headache days at the end of weeks 4 will be compared to baseline. Headache frequency will be described at each time point using the mean, 95% confidence interval, median, and range. Changes from baseline in headache frequency will also be described using the mean, 95% confidence interval, median and range, and assessed using paired t-tests or non-parametric Wilcoxon signed-rank tests as appropriate. Graphical procedures will include plots of average headache frequency over time. The proportion of responders will be computed at week 4. Response at the end of week 4 is the primary endpoint.

Headache hours (moderate/severe pain intensity): Change in the amount of total headache hours (with moderate or severe pain) at the end of week 4 will be compared as separate time points to baseline. Headache hours will be analyzed similar to specific aim #1 as above.

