Acute medication use (# days over weeks 4): Acute medication use at the end of week 4 will be compared as separate time points to baseline. Medication usage will be analyzed similar to specific aim #1 as above.

Remission rate (proportion of patients free of headache weeks 4): The proportion of patients who do not have any occurrence of headache at the end of week 4 will be divided by the total number of evaluable patients in the study. A point estimate and confidence interval will be computed for these endpoints, headache freedom at week 4.

Patient-reported Outcomes: Patients will complete the BDI, STAI, MIDAS, 4-week Follow-up Headache Characteristics and the PGIC. Patient reported outcomes (BDI, STAI, MIDAS) will be scored using published scoring algorithms and described at each time point using the mean, 95% confidence interval, median, and range. Changes from baseline will also be described using the mean, 95% confidence interval, median and range, and assessed using paired t-tests or Wilcoxon signed-rank tests as appropriate. Graphical procedures will include plots of average values over time. The PGIC will be described to assess patient perception of improvement.

Adverse Events Analysis: The proportion of subjects experiencing adverse events, the nature of the adverse events, as well as severity and relationship of the adverse events to the study will be reported using descriptive statistics. The proportion of subjects with adverse events that led to withdrawal from the study will also be reported. All subjects who received at least one dose of erenumab will be included in the safety analysis. The maximum grade for each type of adverse event will be summarized as the number of patients experiencing the event divided by the total number of evaluable patients. Frequency tables will be constructed. Additionally, the relationship of the adverse event(s) to the study treatment will be taken into consideration.

Results Reporting on ClinicalTrials.gov: At study activation, this study will have been registered within the “ClinicalTrials.gov” website. The Primary and Secondary Endpoints (ie, “Outcome Measures”) along with other required information for this study will be reported on ClinicalTrials.gov.

Protocol Approval and Maintenance by IRB

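### The plan does not say how indomethacin restarted after Day 0 is scored, so an erenumab failure who resumes it regularly can count as a responder

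*Combined protocol and SAP*

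**What the plan says.** **Response.** Daily Headache Diary defines a responder by "50% or greater reduction in headache frequency at week 4 post erenumab treatment compared to frequency during the screening phase". Statistical Methods & Analysis repeats this: "patients will be classified as a responder (50% or greater reduction by week 4 post erenumab treatment". Neither text sets a condition on other treatment.

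**Denominator.** Under Primary endpoint & analyses, eligible patients who complete screening and "have initiated treatment with erenumab will be considered evaluable for assessing the primary endpoint". The result is a proportion with a binomial 95% interval.

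**Indomethacin.** Inclusion requires a past or current complete response to it. Exclusion covers "Nonresponse to a therapeutic dose of indomethacin for hemicrania continua when used for at least 1 week". Screening Phase (Day -7) stops indomethacin in anyone taking it preventively. Inclusion also asks for stable prevention with no change foreseen.

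**Acute treatment.** "Patients will be allowed to use acute headache treatments including NSAIDs during the study if needed". Indomethacin, which the background describes as an NSAID, is not excepted. "The use of these treatments will be recorded", and the Schedule of Events collects concomitant medications at week 4.

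**Secondary endpoints.** "Acute medication use at the end of week 4 will be compared as separate time points to baseline". Remission is "The proportion of patients who do not have any occurrence of headache at the end of week 4" divided by all evaluable patients.

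**The concern.** The screening week is collected off preventive indomethacin, and follow-up is not guaranteed to be. The drug that could come back is the one to which every participant is known to respond. The background says that patients usually respond to it within days and that most relapse without it. If erenumab does not work and the patient resumes regular indomethacin, headache frequency falls against a baseline taken without it, and the rule credits the fall to erenumab.

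Aim 1 is the response of hemicrania continua to erenumab. A restart can push the primary rate only upward, and a single-arm design has no control group to subtract it. The analysis is descriptive, so the effect falls on the reported proportion and its interval rather than on a formal test.

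**Working it through.** **The plan's own figure.** Sample Size states 80% power for 20 patients, a difference of 2 days, SD 3 and a two-sided 0.05 paired t-test. Taking 3 as the SD of the paired differences, exact noncentral-t power is 80.7%, so the figure reproduces. Enrolment also reproduces: 20/(1 - 0.20) = 25. These figures supply n = 20 and do not otherwise bear on this point.

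**Effect on the primary rate.** One reclassified patient moves the rate by 1/20 = 5 points. The documents give neither a true response rate nor a restart rate, so both are assumed here. Take 4 true responders and let k of the 16 failures restart early enough to be scored as responders. Intervals are Clopper-Pearson.

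| k | Observed | Rate | 95% CI |
|---|---|---|---|
| 0 | 4/20 | 20% | 5.7-43.7% |
| 1 | 5/20 | 25% | 8.7-49.1% |
| 2 | 6/20 | 30% | 11.9-54.3% |
| 4 | 8/20 | 40% | 19.1-63.9% |

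If erenumab had no effect at all, five such restarts would read as 5/20 (8.7-49.1%) instead of 0/20 (0-16.8%).

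**How late a restart still counts.** Let r be the restart day and L the days until indomethacin works. Assume 7/7 headache days at screening, daily headache through day r+L-1, and none afterwards. The plan can be read as assessing Days 22-28 or Days 1-28.

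- Response, Days 22-28: headache days are r+L-22 and must be at most 3, so r ≤ 25-L.
- Response, Days 1-28: headache days are r+L-1 and must be at most 14, so r ≤ 15-L.
- Remission, Days 22-28: r+L-22 must be at most 0, so r ≤ 22-L. Over Days 1-28 remission is not possible.

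| L (days) | Response, Days 22-28 | Response, Days 1-28 | Remission, Days 22-28 |
|---|---|---|---|
| 1 | Day 24 | Day 14 | Day 21 |
| 2 | Day 23 | Day 13 | Day 20 |
| 3 | Day 22 | Day 12 | Day 19 |
| 7 | Day 18 | Day 8 | Day 15 |

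L = 7 is the period after which the exclusion criteria allow nonresponse to be judged. Under either window there is time for a patient to find that erenumab has failed, restart, and still meet the rule.

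**As-needed doses.** Assume that a dose clears only the day it is taken and that every other day has headache. With 0, 1 or 2 dose days in the screening week, the baseline is 7, 6 or 5 of 7. A 50% reduction then allows at most 3, 3 or 2 headache days in Days 22-28, which takes 4, 4 or 5 dose days. Over Days 1-28 with no screening doses it takes 14 of 28. Occasional doses do not create a response. Stable acute use lowers the baseline as well, so only a restart or an increase after Day 0 inflates the rate.

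**The case against.** The strongest reply is that the plan does deal with indomethacin. It stops preventive use at Day -7, requires stable prevention at entry, records acute use and analyses it. The acute-treatment paragraph permits acute use, not resumed prevention, so a regular restart can be read as a departure from the plan, and non-compliance is reportable to the IRB. With about 20 patients, a listing would reveal every restart. The frequency is also unsupported: the background says tolerability limits indomethacin, and some entrants may have stopped it long before.

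Most of this stands as a limit on scope. A reader might infer that nothing in the plan covers indomethacin after Day 0; the stop, the entry criterion and the recording show otherwise. A reader might also infer that permitting NSAIDs is enough to produce responders, or that the rate will be badly inflated. The as-needed arithmetic does not support the first inference, and the documents give no restart rate to support the second.

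The timing limits are also idealised. The secondary headache-day definition counts only days with more than 4 hours of moderate or severe pain. If it also governs frequency, which is unclear, a 7/7 baseline is not assured and the limits shift.

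The scoring gap remains. None of these provisions changes responder status, and no planned analysis links medication records to it. A patient who departs from the plan in this way is still evaluable and is still scored on frequency alone. Deciding how to treat such a patient after seeing open-label results is weaker than a rule fixed beforehand.

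**Conclusion.** The concern holds in a limited form. The plan shows an intent to keep preventive indomethacin out but states no bar on restarting it and no scoring consequence. Followed as written, the responder rule can credit erenumab with the effect of resumed regular indomethacin, and the remission rate has the same weakness if the window is week 4 only.

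The direction is upward and the size is 5 points per patient at n=20. The total cannot be derived from the documents and may be nil. The conclusion rests on resumption being regular and early enough for the drug to act, and on the patient responding to it as the entry criterion requires. It does not extend to occasional doses, to the sample size or to any formal test. Because the change is cheap and the primary estimate has no comparator, the sponsor should make it.

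**What to change.** 1. **Acute Headache Therapy.** State that indomethacin should not be used as acute treatment from Day -7 to Day 28. If it is clinically needed, the patient stays in the study and the dates are recorded. Starting at Day -7 puts baseline and follow-up under one rule.
2. **Primary endpoint & analyses, and Remission rate.** A patient who resumes scheduled (daily) indomethacin before the end of week 4 is a non-responder and not in remission. For any other indomethacin use, each dose day counts as a headache day, both in the screening week and in the assessment window, whichever window applies.
3. **Sensitivity analysis.** Report the rate from the diary alone, regardless of indomethacin, with the number of patients reclassified.

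A rule that fails a patient for any single dose would overcorrect. Someone who goes from 7/7 to 1/7 headache days with one dose on another day scores 2/7 under item 2, a reduction of 5/7 = 71%, and remains a responder. No carry-over margin is proposed, because the documents give no duration of effect.

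The cost is two short rules and one extra line of output, plus a check that the records capture drug and date; the plan says that use is recorded but not in what detail. Sample size and visits do not change. The reported rate may be slightly lower, a dose day in the window rules out remission, and an occasional true responder may be counted as a failure. The sensitivity analysis shows how many patients are affected.

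### The primary response definition does not name its counting unit, and the protocol allows response to be redefined once outcomes are known

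*Combined protocol and SAP*

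**What the plan says.** The primary rule appears twice. The Daily Headache Diary section defines a responder by "50% or greater reduction in headache frequency at week 4 post erenumab treatment compared to frequency during the screening phase". Statistical Methods & Analysis repeats the 50% cut and calls a patient a responder "or a non-responder (less than 50% reduction in headache frequency". Neither place gives a unit, an intensity threshold or a duration threshold. Under Analysis Plans, the primary endpoint is the proportion with a response as defined earlier in that section, with a binomial 95% confidence interval.

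The only quantified headache day is in a secondary heading under Analysis Plans: "Headache days (>4 hours moderate/severe pain) weeks 4 compared to baseline". The text below it uses headache frequency as the name of the quantity: "Headache frequency will be described at each time point using the mean, 95% confidence interval, median, and range". It then adds: "The proportion of responders will be computed at week 4. Response at the end of week 4 is the primary endpoint".

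Other measures appear elsewhere. The Sample Size paragraph refers to the frequency of headache days in a 28-day period, with no threshold. A further secondary endpoint is "Change in the amount of total headache hours (with moderate or severe pain) at the end of week 4". The remission endpoint requires no headache at all.

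The Daily Headache Diary section closes by noting that outcomes are measured at 4 weeks, where most trials use 12, and that "depending upon patient outcomes other definitions of “response” and “non-response” could be used".

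**The concern.** A 50% reduction has a fixed meaning only when the quantity being reduced is fixed. In this plan the unit can be inferred from a secondary paragraph but is not part of the primary definition. That alone would be a small drafting gap. It matters more because the protocol lets the response definition depend on patient outcomes.

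The trial is single-arm and open-label, and its headline result is one proportion with its interval. If the definition may be settled after the diaries have been seen, that proportion has no pre-specified meaning, and a favourable choice would bias it upwards. The binomial interval does not allow for such a choice.

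The unit is a plausible place for this to happen. If some pain is present on most days, a count of any-headache days starts near its ceiling and gives no credit for a fall in intensity, whereas a count of moderate or severe days does.

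**Working it through.** **The plan's own figure.** The sample-size paragraph gives n = 20, a fall of 2 headache days per 28, SD 3, a paired t-test and two-sided alpha 0.05. The noncentrality is (2/3) × √20 = 2.98 with 19 degrees of freedom, which gives power of 80.7% against the stated 80%. The figure reproduces. It does not help to identify the unit, because the paragraph gives no threshold for a headache day.

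**One patient, two units.** Assume some headache on all 7 days of both weeks.
- Any-headache days go from 7 to 7. The reduction is 1 − 7/7 = 0%, so the patient is a non-responder.
- Days with more than 4 hours of moderate or severe pain go from 7 to 2. The reduction is 1 − 2/7 = 71%, so the patient is a responder.

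**Response rate under each unit.** The documents give no baseline frequency, so these inputs are assumptions:
- some pain on every day before and after treatment;
- independent days;
- one 7-day window at screening and one at follow-up;
- qualifying days (more than 4 hours of moderate or severe pain) on 70% of baseline days.

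Let B ~ Bin(7, 0.70) be the qualifying days at screening and X ~ Bin(7, p) those at follow-up. The response rate is P(X ≤ B/2 | B > 0).

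| Qualifying days fall from 70% to | Fall in days per 28 | Responders, implied unit | Responders, any-headache days |
|---|---|---|---|
| 60% | 0.10 × 28 = 2.8 | 15% | 0% |
| 50% | 0.20 × 28 = 5.6 | 30% | 0% |
| 40% | 0.30 × 28 = 8.4 | 48% | 0% |
| 30% | 0.40 × 28 = 11.2 | 68% | 0% |
| 20% | 0.50 × 28 = 14.0 | 85% | 0% |

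The 0% column is not a finding. It follows directly from assuming pain every day before and after treatment.

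**Precision at n = 20.** An observed 14/20 has an exact 95% interval of 45.7% to 88.1%, and 0/20 has 0% to 16.8%. With a large effect confined to moderate or severe pain, the two units would give intervals that do not overlap. With a small effect the intervals do overlap: 3/20 (15%) has an interval of 3.2% to 37.9%.

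**Patients with no qualifying day at screening.** The calculation conditions on B > 0 because the percentage reduction is otherwise undefined. Under the assumed 70% rate this is rare (0.3^7 = 0.0002). However, the eligibility criteria set no minimum number of moderate or severe days, so real patients could fall in this group, and the plan has no rule for them.

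**The case against.** The strongest case against is that the unit is already there. The paragraph headed by the >4-hour threshold uses headache frequency for that quantity, and in the same place says that the responder proportion is computed and is the primary endpoint. The natural reading is that response is counted in those days. No text defines the primary as any-headache days.

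That stands, and it rules out a stronger reading that a reader might infer: that the primary and the secondary endpoint use two competing units. The documents support only an implied unit that was not carried into the primary definition. The implication is not a definition, because the primary endpoint points back to text with no threshold and the sample-size wording has none.

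It is also fair that daily pain is an assumption. The visible text rests on the disease name and the ICHD-3 reference. The largest contrasts need effects well above the 2 days per 28 used for planning; the smallest case in the table, 2.8 days per 28, gives 15% against 0%. A reader might infer that the response rate will swing from nothing to a majority. The documents give no basis for that, since it needs a large fall in moderate or severe pain while milder pain persists on every day.

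Finally, the analysis is descriptive, and days, hours and remission are all to be reported, so much of any divergence would be visible. That limits the harm but does not remove it, because the primary proportion is the result that will be quoted. Nothing here implies that the analysts would choose in bad faith. The problem is that the written rule permits the choice.

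**Conclusion.** The point holds as a weakness in pre-specification. The response unit is implied but missing from the primary definition, and an explicit sentence lets the definition depend on outcomes. Of the two, the sentence is the more serious, because it would leave the headline proportion open even if the unit were named.

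The possible size runs from a gap of about 15 percentage points (qualifying days falling from 70% to 60%) to about 85 points (to 20%). These figures rest on daily pain before and after treatment, independent days, 7-day windows and a 70% baseline rate, none of which the documents give. The gap shrinks as background pain clears, because the two units then converge. The figures show how much the choice of unit could matter. They do not predict the result.

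**What to change.** 1. In Daily Headache Diary, delete the sentence that allows response to be redefined according to outcomes. Alternatively, state that any other definition is post hoc and cannot replace the primary one.
2. In both primary definitions (Daily Headache Diary and Statistical Methods & Analysis), write in the unit that the plan already implies: diary days with more than 4 hours of moderate or severe pain.
3. Use the same unit in the Sample Size paragraph.
4. Add any-headache days as a secondary measure.
5. Count a patient with no qualifying days in the screening week as a non-responder in the primary analysis, with a sensitivity analysis that excludes such patients.

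The change is a few sentences, and the intensity and duration threshold is already in the plan. The cost is that the primary endpoint will not credit changes in mild background pain. Remission captures only complete freedom from headache, so partial change in mild pain would be seen only in the added any-headache-days measure.

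### Efficacy is to be judged against a clinical threshold that is never given a value, and the definition of response may change with the outcomes, so both can be set after the data are seen

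*Combined protocol and SAP*

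**What the plan says.** Four places in the combined protocol and SAP bear on how efficacy will be judged.

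- **Statistical Methods & Analysis, opening paragraph:** "The analysis will be kept descriptive and efficacy will be evaluated based on clinical meaningfulness threshold". No number, scale or endpoint follows.
- **Daily Headache Diary:** a responder is a patient with "50% or greater reduction in headache frequency at week 4 post erenumab treatment compared to frequency during the screening phase". The same paragraph notes that outcomes are measured at 4 weeks rather than the more usual 12. It then adds that, "depending upon patient outcomes other definitions of" response and non-response could be used.
- **Analysis Plans, primary endpoint:** the responder proportion among evaluable patients, with a point estimate and a two-sided 95% binomial interval. No reference or target proportion is given. Change in headache days, tested by paired t-test or signed-rank test, is listed among the secondary endpoints.
- **Sample Size:** 20 patients give "80% power to detect a decrease of frequency of headache days (in 28-day period) of 2 or more from baseline". This figure is for a paired t-test at two-sided alpha 0.05, with the SD taken as 3.

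**The concern.** The plan announces a decision rule for efficacy and leaves it blank. The 50% figure says when one patient counts as a responder. It does not say what proportion of responders, or what confidence limit, would mean that the drug works.

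The sentence in the diary section makes this more than missing detail, because it expressly ties the choice of definition to the results. With no comparator and no blinding, the responder proportion has to be read against some outside standard. If both the standard and the definition are open until the outcomes are in, a favourable conclusion carries little weight: the reader cannot tell whether the bar was set before the result or fitted to it.

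**Working it through.** **1. Reproduce the plan's own figure.** Inputs from Sample Size: n = 20, mean change 2 days per 28, SD 3 (read as the SD of the paired change), two-sided alpha 0.05. For a paired t-test, df = 19 and the noncentrality is (2/3) × √20 = 2.98. The noncentral t distribution gives power of 80.7%, against the stated 80%. The calculation is sound for that test.

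**2. Can the 2-day figure serve as the missing bar?** It is a group mean, while the primary endpoint is a proportion of patients. Converting one to the other needs a baseline frequency, which the documents do not give. Assume that each patient has b headache days per 28 at baseline and that changes are normal with mean −2 and SD 3. The chance that a patient reaches a 50% reduction is then Φ((2 − b/2)/3).

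| Assumed baseline b (days per 28) | 50% reduction (days) | Chance of response | Expected responders of 20 |
|---|---|---|---|
| 28 | 14 | 0.00003 | 0.0006 |
| 20 | 10 | 0.004 | 0.08 |
| 16 | 8 | 0.023 | 0.5 |
| 12 | 6 | 0.091 | 1.8 |
| 8 | 4 | 0.252 | 5.0 |

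The implied responder rate runs from almost nil to about 25%, depending on an undocumented baseline. The sample size section therefore does not supply a bar for the primary endpoint.

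**3. How much depends on the bar?** The plan asks for a 95% interval based on the binomial distribution; I take the exact (Clopper-Pearson) form. With x responders of n, the lower limit is the 2.5th percentile of Beta(x, n − x + 1). The smallest x whose lower limit exceeds each reference rate at n = 20 is:

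| Reference rate | Responders needed of 20 | Lower limit at that count | Lower limit with one fewer | Chance of meeting the bar if the true rate is 50% |
|---|---|---|---|---|
| 10% | 6 | 11.9% | 8.7% | 98% |
| 20% | 9 | 23.1% | 19.1% | 75% |
| 30% | 11 | 31.5% | 27.2% | 41% |
| 40% | 13 | 40.8% | 36.1% | 13% |
| 50% | 15 | 50.9% | 45.7% | 2% |

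The last column is the binomial probability P(X ≥ x) with n = 20 and p = 0.5.

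Two results show the effect. Nine of 20 (45%, interval 23.1% to 68.5%) clears a 20% bar and fails a 30% bar. Eight of 20 (40%, interval 19.1% to 63.9%) clears 10% and fails 20%.

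Up to 25 patients may be evaluable. By the same formula the counts at n = 25 are 7, 10, 13, 16 and 18, with lower limits of 12.1%, 21.1%, 31.3%, 42.5% and 50.6%.

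**4. The movable definition.** No arithmetic is possible here, because the alternative definitions are not listed. Any effect would come on top of step 3, since changing the definition changes x itself.

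**The case against.** The strongest reply is that this is a small exploratory study. The same sentence says that the analysis will be descriptive, and estimating a proportion with its interval is a legitimate aim without a pass mark. That stands, and the fix allows it. It does not rescue the present text, which also says that efficacy will be evaluated against a threshold.

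A second reply is that the threshold simply is the 50% reduction. On that reading there is still no proportion of responders that counts as success, and the diary section lets the 50% cut itself move.

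A third reply is that much is already fixed: the 50% cut in both sections, the denominator (eligible patients who completed screening and started erenumab) and the 95% interval. This also stands. A reader might infer that the same data could support either conclusion. That goes too far, because the specified estimate and interval would be reported whatever label is attached. The freedom lies in the interpretation and, through the diary sentence, in the definition.

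A reader might also infer that the plan's two effect sizes contradict each other sevenfold, since 50% of 28 days is 14 days and 14/2 = 7. The documents do not support this. The 2 days is a mean change that a test on a secondary endpoint can detect, and the 50% is a cut for a single patient. Neither is offered as the efficacy threshold. Seven is also the largest possible ratio, reached only with headache on all 28 days. A headache day in the Analysis Plans needs more than 4 hours of moderate or severe pain, so the baseline may be lower: the ratio is 4 at 16 days, 2 at 8 days and 1 at 4 days.

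**Conclusion.** The concern holds in this form: the stated basis for judging efficacy is undefined, and the definition of response may be changed in the light of the outcomes. Both should be settled before the first dose.

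On the primary endpoint, the open bar spans 6 to 15 responders of 20 for reference rates of 10% to 50%. The chance of a favourable verdict at a true response rate of 50% moves from 98% to 2% across that range. These figures assume 20 evaluable patients, exact intervals and a rule based on the lower 95% limit. The reference rates are illustrative, because the documents give none. The power calculation is not in error; it belongs to a different endpoint.

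The finding rests on the protocol text available here, which lacks the opening of the document. It shows that the plan permits an outcome-driven conclusion. It does not show that one is intended.

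**What to change.** 1. **Daily Headache Diary:** delete the sentence that allows other definitions depending on outcomes. Keep the reduction of 50% or more as the only primary definition, and state that any other definition will be labelled exploratory and post hoc.

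2. **Statistical Methods & Analysis:** choose one of two options.
   - *Estimation only.* Delete the threshold clause and report the responder proportion with its exact two-sided 95% interval.
   - *A stated bar.* Before the first dose, name one reference responder rate, justify it, and require the lower 95% limit to exceed it. State the rule on the limit itself, since the count needed depends on how many patients are evaluable (for a 20% reference, 9 of 20 or 10 of 25).

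I do not propose a value for the reference rate, because the documents give no basis for one. Chance variation in the diary is an unstable guide. Assuming independent days, and comparing one 7-day week with another, it alone yields a 50% reduction in about 28% of patients with headache on 30% of days, 16% at half of days, and none at a daily baseline. At half of days it falls to about 4% if the comparison uses all 28 follow-up days. It also ignores open-label expectation and regression to the mean. The sponsor has to argue the rate from sources outside this plan.

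The cost is a few sentences and the freedom to choose the definition or the bar later. No visit, measurement or patient number changes. If a bar is set, the table in the working shows what it costs in the chance of success: a 20% reference at n = 20 gives 75% at a true rate of 50%, with a 1.0% chance of passing if the true rate is exactly 20%.
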